#### **21.4.4. Intraocular Pressure (IOP)**

IOP will be measured for each eye using applanation tonometry at Day 1, Month 12 and Post-Baseline PRN Treatment Visits prior to evaluation of need for treatment. If DE-109 is administered, a second assessment will be made 40 ( $\pm 10$ ) minutes after injection.

The examiner will measure IOP and record results in mmHg with one decimal place (e.g., 24.0). A single measurement is made to obtain a determination of intraocular pressure. The same contact tonometer employing the Investigator's standard technique, will be used throughout the study. In addition, all reasonable efforts should be made to have the same examiner obtain all IOP measurements for a given subject.

The tonometer must be calibrated for accuracy before the first subject undergoes screening, and at least once every 30 days thereafter, until the last subject has exited the study. For checking calibration, follow the manufacturer's instructions. If when checked, the variation is within  $\pm 2$  mmHg, the tonometer is considered adequately calibrated. However, if the variation exceeds this amount, the tonometer should be sent for repair and a different, adequately calibrated instrument should be used for IOP measurement. The date of each calibration, along with the name and signature (or initials) of the person who performed the calibration, must be documented. The tonometer calibration record will be retained as a part of the study record.

#### **21.4.5. Indirect ophthalmoscopy**

An indirect ophthalmoscopy will be performed at Day 1, Month 12 and Post-Baseline PRN Treatment Visits to examine the retina of each eye. Indirect ophthalmoscopy will be performed prior to each study drug injection and then again within 30 minutes after study drug injection. Assessments include lens, retina, macula, choroid, and optic nerve. Lens will be assessed for the presence or absence of cataract prior to study drug administration. All other assessments will be noted as normal or abnormal.

#### **21.4.6. Vitreous Haze**

VH will be assessed for each eye according to the Investigator's standard practice at Day 1, Month 12 and Post-Baseline PRN Treatment Visits using the modified SUN scale:

0	No inflammation
0.5+	Trace Inflammation (slight blurring of the optic disc margins and or loss of nerve fiber layer reflex)
1+	Mild blurring of the retinal vessels and optic nerve
1.5+	Optic nerve head and posterior retina view obstruction greater than 1+ but less than 2+
2+	Moderate blurring of the optic nerve head
3+	Marked blurring of the optic nerve head
4+	Optic Nerve head not visible

### **21.5. Appendix E – Manual SAE Reporting Process**

In the event the EDC system is unavailable and your site needs to report a SAE, please follow the manual process described below.

- Complete both the paper AE and SAE forms (located in your site regulatory binder)
- Attach a Fax Cover Sheet with your contact information and address to Santen Drug Safety
- Fax the Cover Sheet, AE form and SAE form to Santen at the appropriate fax number identified below.

For SAE supporting information (i.e. xray reports, hospital summaries etc.) that are not included in the EDC format, follow the same reporting process as for manual SAE reporting.

**Table 5:** SAE Manual Reporting Fax numbers

## ABBREVIATIONS

AE(s)	Adverse Event(s)
ATC	Anatomical-Therapeutic-Chemical
BCVA	Best-Corrected Visual Acuity
CDISC	Clinical Data Interchange Standards Consortium
CSR	Clinical Study Report
eCRF	Electronic Case Report Form
EMEA	Europe, the Middle East and Africa
ESI(s)	Event(s) of Special Interest
ETDRS	Early Treatment Diabetic Retinopathy Study
IOP	Intraocular Pressure
MedDRA	Medical Dictionary for Regulatory Activities
mmHg	Millimeter of Mercury
OCT	Optical Coherence Tomography
OD	Oculus Dexter (right eye)
OS	Oculus Sinister (left eye)
OU	Oculus Uterque (both eyes)
PRN	Pro Re Nata (as needed)
SAE(s)	Serious Adverse Event(s)
SAKURA	Santen Protocol 32-007
SAP	Statistical Analysis Plan
SAR(s)	Suspected Adverse Reaction(s)
SAS	Statistical Analysis System
SOC	System Organ Classification
SUN	Standardized Uveitis Nomenclature
US	United States
VH	Vitreous Haze
WHO-DDE	World Health Organization Drug Dictionary Enhanced

## 1. INTRODUCTION

This statistical analysis plan (SAP) specifies the statistical methods to be implemented for the analysis of data collected within the scope of Santen's Protocol 32-009 (SPRING), "A Phase IIIb, Multinational, Multicenter, Open-Label Extension Study Assessing the Long-Term Safety of PRN Intravitreal Injections of DE-109 in Subjects with Non-Infectious Uveitis of the Posterior Segment of the Eye Who Have Participated in the SAKURA Development Program".

This SAP applies to the study protocol 32-009 US Amendment 01 dated 02 June 2016 and provides details of the descriptive statistical analyses of data collected from this Open-Label study. Results from the descriptive statistical analyses will become the basis of the Clinical Study Report (CSR) for Protocol 32-009.

## 2. STUDY OBJECTIVE

The objective of this extension study is to evaluate the long-term safety of treatment with DE-109 (440 µg) in subjects with non-infectious uveitis of the posterior segment of the eye.

## 3. STUDY DESIGN

### 3.1. General Study Design

This is a multicenter, open-label, extension study of intravitreal injections of the 440 µg dose of DE-109 in subjects with non-infectious uveitis of the posterior segment who received any dose of DE-109 and exited the SAKURA program under Santen Protocol 32-007. In addition, subjects who were randomized and received at least two injections of DE-109 during the first five months of the SAKURA study and obtained clinical benefit from the study medication, as determined by the Investigator, may be considered for entry in this 12-month extension study. The minimum time lag from last injection in the SAKURA program to entry into the SPRING program is 60 days. Any subjects can enter into protocol 32-009 US Amendment 01 if that subject is from U.S. and the time lag from exiting the SAKURA program to entry into protocol 32-009 is no more than 6 months.

Each subject retains the same subject ID as had been previously assigned in the SAKURA program. The study eye to be treated in this extension study is the same as the eye treated during the SAKURA program.

Study assessments are conducted for all subjects at Day 1 (Baseline), Month 2, Month 4, Month 6, Month 8, Month 10 and Month 12. Additional visits may be conducted according to the Investigator's standard clinical practice at interim unscheduled visits. DE-109 treatment may be administered in the study eye at the Investigator's discretion on Day 1 and/or any of the Post-Baseline PRN Treatment Visits at Month 2-10 but no more frequently than every 60 days. Treatment of the fellow eye with alternative local therapies is at the Investigator's discretion. However, administration of DE-109 to the fellow eye is a protocol deviation, and is counted as such.

### 3.2. Randomization and Masking

This is an open-label study. Randomization is not employed in this study. At the investigator's discretion, an injection of DE-109 (440 µg) may be administered. The study drug container has a unique number and is dispensed in sequential ascending order by each center.

### 3.3. Sample Size Planning

There is no statistical consideration regarding the sample size. The original defined number of subjects for SPRING study was approximately 200 subjects. Due to slow enrolment, the sample size has been adjusted to 60 subjects. The enrollment was completed by 18 November 2016. Of the 60 subjects, 13 signed the consent of Protocol US Amendment 01.

### 3.4. Visits and Assessments

The assessments to be conducted at each visit can be found in Table 1.

**Table 1 Assessment Schedule**

	Day 1 Screening/ Baseline	Post-Baseline PRN Treatment Visits	Month 2/4/6/8/10 Post-Baseline PRN Treatment Visits h	Month 12 or Early Termination d
Assessment window (Days)	-	≥60 days since last injection	±7 Note: ≥60 days since last injection	±14
Informed consent a	x			
Demographics	x			
Medical/surgical history	x			
Medications	x	x	x	x
Urine pregnancy test, if appropriate	x b	x b	x b	x b
Inclusion/exclusion criteria	x			
Best-corrected visual acuity	x	x	x	x
Intraocular pressure	x c	x c	x c	x c
Indirect ophthalmoscopy e	x	x	x	x
Vitreous haze	x	x	x	x

	Day 1 Screening/ Baseline	Post-Baseline PRN Treatment Visits	Month 2/4/6/8/10 Post-Baseline PRN Treatment Visits h	Month 12 or Early Termination d
Slit lamp biomicroscopy h	x	x	x	x
DE-109 administration, if needed (PRN)	x	x	x	
Endothelial cell count (only at selected sites) h	x	x	x	x
Adverse events	x f	x f	x f	x f
Imaging h : OCT (including CRT), FA, FP	x g	x g	x g	x g

## Abbreviations:

a Informed consent is be obtained prior to conducting any study-related activities.

b Urine pregnancy tests are to be performed on all women of childbearing potential.

c On days when DE-109 injections are administered, perform IOP before and 40 ( $\pm 10$ ) minutes after DE-109 injection.

d For Early Termination Visits please complete the procedures for the Month 12 visit.

**Error! Reference source not found.** Indirect ophthalmoscopy is performed prior to each study drug injection and then again within 30 minutes after study drug injection.

**Error! Reference source not found.** On days when DE-109 injections are administered AEs are elicited before and after DE-109 injection.

e Performed at investigator's discretion.

h For subjects under Protocol US Amendment 01 only.

## 4. DEFINITIONS

### 4.1. Time-Related Terms

#### 4.1.1. Baseline Visit

The *baseline visit* of the SPRING study is the first scheduled visit on Day 1.

#### 4.1.2. Study Exit Visit

The *study exit visit* of the SPRING study is the Month 12 visit or early termination visit. If both are missing, the last visit before exit date will be considered as study exit visit. For subjects who don't have any visits after Day 1, Day 1 visit will be considered as both Baseline Visit and Study Exit Visit.

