### 7.5.1. Visit 1 - Day 1 - Screening/Baseline

- Explain the purpose and details of the study to the subject and obtain written informed consent prior to the subject's participation in any extension study related activity.
- Determine if the subject has:
  - A subject number from participation in the SAKURA program, Amendment 05
  - Received at least two treatments of DE-109 in the first five months of the SAKURA program
  - Received clinical benefit from treatment with DE-109 as determined by the Investigator.
- Record subject's demographics, medical and surgical history and medications.
- If the subject is a woman of child-bearing potential, perform a urine pregnancy test.
- Review the inclusion and exclusion criteria. If the subject has met the inclusion/exclusion criteria, the subject may continue in the study.
- Perform the following assessments:

**For subjects exiting the SAKURA program at this visit, the following assessments will be obtained from the SAKURA Termination Visit. Please skip to "Evaluation of Need for Treatment."**

- BCVA
- IOP
- Indirect ophthalmoscopy
- VH.
- **Evaluation of Need for Treatment** - If in the judgment of the investigator, the subject needs DE-109 treatment, it has been at least 60 days since the last treatment, and the results of the urine pregnancy test were negative (for women of child-bearing potential), perform the study drug administration procedures as described in Section [10.4](#) and [10.5](#).
- The following assessments must be performed after the administration of study drug:
  - Indirect ophthalmoscopy within 30 minutes following injection
  - IOP 40 ( $\pm 10$ ) minutes following injection
  - AEs

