### 4.2.3. Change from Baseline

The *change from baseline* in a measure at a post-baseline visit will be derived as:

Change from Baseline at a Post-Baseline Visit = (Score at the Post-Baseline Visit) – (Baseline Score).

For any measure assessed before and after injection at visits, only the pre-injection scores will be used to derive the change-from-baseline variable.

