## 6. GENERAL CONSIDERATIONS

All variables will be summarized by the last dose received in SAKURA study and overall. Continuous variables will be summarized using descriptive statistics such as number of observations (n), mean, standard deviation, medium, minimum, and maximum. Categorical variables will be tabulated using frequency (n) and percent (%).

All data manipulations and descriptive summaries will be performed using SAS Version 9.4 or later.

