## 6.2. Handling of Missing Data

### 6.2.1. Safety Measures

Descriptive summaries of safety measures will be based on observed data only. No imputation of missing scores will be implemented.

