## **8.2. Vitreous Haze (VH)**

VH score, change from baseline, and shift from baseline in VH at Month 12 visit and Study Exit visit will be summarized and listed.

Subgroup analysis will be performed for change from baseline in study eye at study exit by demographics and baseline characteristics in [Section 7.2](#).

Subjects with any score of 3+ or above in VH after Baseline will be listed.

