## **8.4. Intraocular Pressure (IOP)**

IOP, change from baseline in IOP at the Study Exit visit, and change after injection in IOP will be summarized.

Subjects with elevated IOP reported as an AE will be tabulated. Subjects with any increase of  $\geq 10$  mmHg in IOP from baseline at any post-baseline visit, or after injection will be tabulated and listed. In addition, Subjects with IOP of at least 25, 30, or 35 mmHg at any post-baseline visit will be summarized.

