### **8.5. Indirect Ophthalmoscopy**

For retina, macula, choroid, and optic nerve, shift from baseline in status (Normal or Abnormal) will be summarized at study exit visit and shift after injection will be summarized by injection visit. Subjects with any change from normal at baseline to abnormal in status after baseline will be listed.

For phakic lens only, shift from baseline in presence of cataract (Yes or No) at study exit visit will be summarized. Subjects with no cataract presence at baseline to cataract presence after baseline, if any, will be listed.

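### SAP 4.1.2 makes Day 1 the Study Exit Visit for subjects never seen again, so they appear in the exit score and shift tables as unchanged

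*SAP*

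**What the plan says.** SAP 4.1.2 defines the Study Exit Visit as the Month 12 or early termination visit. If both are missing, it is the last visit before the exit date. For subjects with nothing after Day 1, it adds that the "Day 1 visit will be considered as both Baseline Visit and Study Exit Visit".

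The exit visit is then used as follows:

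- **Vitreous haze (SAP 8.2):** score, change and shift at Month 12 and at Study Exit. In addition, "Subgroup analysis will be performed for change from baseline in study eye at study exit by demographics and baseline characteristics".
- **BCVA (SAP 8.3):** score and change at Month 12 and at Study Exit.
- **IOP (SAP 8.4):** "IOP, change from baseline in IOP at the Study Exit visit, and change after injection in IOP will be summarized".
- **Ophthalmoscopy and cataract (SAP 8.5):** "For retina, macula, choroid, and optic nerve, shift from baseline in status (Normal or Abnormal) will be summarized at study exit visit"; cataract shift in phakic eyes is also summarised at study exit.

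Three other rules bear on this. SAP 4.2.3 introduces change from baseline with the words "in a measure at a post-baseline visit will be derived as". SAP 6.2.1 states: "Descriptive summaries of safety measures will be based on observed data only. No imputation of missing scores will be implemented". SAP 6 adds: "All variables will be summarized by the last dose received in SAKURA study and overall".

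On where the Day 1 values come from, Protocol 7.5.1 says: "For subjects exiting the SAKURA program at this visit, the following assessments will be obtained from the SAKURA Termination Visit". The assessments concerned are BCVA, IOP, indirect ophthalmoscopy and vitreous haze.

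**The concern.** A subject with no follow-up has an unknown outcome after entry. Under the SAP 4.1.2 rule that subject is displayed at exit as having been assessed and found unchanged. In effect this carries the baseline value forward to exit, although no missing score is formally imputed.

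Long-term safety is the study's only objective. Change in IOP and the ophthalmoscopy and cataract shifts from baseline are summarised at Study Exit with no Month 12 counterpart, so no parallel summary would show the effect. For the shift tables the direction is known: the percentage with a new abnormality or a new cataract is lowered. For the exit scores, baseline values from unfollowed subjects are mixed with true follow-up values, and the direction is not known.

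For subjects who leave SAKURA on the day they enter this study, the reported exit value would be a parent-study measurement taken before any injection in the extension.

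**Working it through.** The SAP gives no figure to reproduce here, because the study is descriptive. The check follows the definitions and then computes the size of the effect.

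**Step 1: which record is used at exit.** SAP 4.2.2 takes the baseline score from Day 1, before the injection if one is given. SAP 4.1.2 takes the exit visit from the same day. Exit minus baseline is therefore 0, and exit status equals baseline status, provided the pre-injection record is used. SAP 4.2.3 fixes the pre-injection record for change; nothing fixes it for shift.

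**Step 2: whether these subjects are removed anywhere.** The Safety Population (SAP 5.1) keeps every enrolled subject with any safety data, injected or not. SAP 8.2 to 8.5 contain no exclusion.

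**Step 3: which outputs are reached.**

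| Output at Study Exit | Effect of a Day 1-only subject |
|---|---|
| VH, BCVA and IOP scores | baseline value counted as exit value |
| VH, retina, macula, choroid, optic nerve and cataract shifts | counted as no shift |
| VH, BCVA and IOP change; VH subgroup change | missing if 4.2.3 governs, 0 if 4.1.2 governs; not stated |

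Not reached:
- Month 12 summaries of VH and BCVA, because Table 2 maps only study days of 308 or later to Month 12.
- IOP tabulations at any post-baseline visit.
- Listings of normal-to-abnormal changes and new cataracts.
- AE tables.

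**Step 4: whether the case can occur.** The supplied protocol requires assessments only at Day 1 and Month 12 (Protocol 7.1). SAP 3.3 gives 60 subjects, of whom 13 consented to the US amendment with scheduled Month 2 to 10 visits. That leaves 60 − 13 = 47 without those visits. Against this, Protocol 8.3 asks for the Month 12 assessments at discontinuation where possible.

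**Step 5: size.** Let n be the number in the table and k the number of Day 1-only subjects among them. If s of the n − k followed subjects shift, the table shows s/n instead of s/(n − k). The ratio is (n − k)/n, and a mean change is multiplied by the same factor if zeros are counted. Since k is not given, a range is assumed:

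| n | k | (n − k)/n |
|---|---|---|
| 60 (overall) | 0 | 60/60 = 1.00 |
| 60 | 1 | 59/60 = 0.983 |
| 60 | 3 | 57/60 = 0.95 |
| 60 | 6 | 54/60 = 0.90 |
| 20 (assumed dose group) | 1 | 19/20 = 0.95 |
| 20 | 3 | 17/20 = 0.85 |
| 10 (assumed subgroup) | 1 | 9/10 = 0.90 |

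The group of 20 assumes that the 60 subjects divide equally over the three SAKURA doses; actual group sizes are not given. As an illustration with k = 6, 6 shifts among 54 followed subjects is 6/54 = 11.1%, shown as 6/60 = 10.0%.

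**The case against.** The strongest reply concerns change from baseline. SAP 4.2.3 restricts change to post-baseline visits, and Table 2 starts the first post-baseline window at Day 2. On the most natural reading a Day 1-only subject has no change value, so IOP change and the VH subgroup analysis would be unaffected. Shift could be read as the categorical form of change and limited in the same way. The SAP also refers to ADaM specifications, not supplied here, for detailed visit definitions.

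Further, k may be 0, and at n = 60 one subject has little effect. The larger factors need assumed group sizes. No test or decision rule depends on these tables. SAP 7.1 lists Month 12 non-completers by subject, and the Day 1 value is an observed value, so no imputation rule is broken in the strict sense. Finally, dropping these subjects does not recover their outcomes.

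Much of this stands. The natural reading of 4.2.3 does leave change undefined, the size is unknown, and the affected outputs are limited. It does not answer the point for exit scores, which 4.2.3 does not mention, or for shifts, which the SAP never defines. Nor does it explain what SAP 4.1.2 is for: naming Day 1 as an exit visit has a use only if an exit record is wanted for these subjects. The value is observed, but it was not observed at exit. Listing non-completers elsewhere does not correct the denominator of a shift table.

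**Conclusion.** The concern holds. Applied as written, SAP 4.1.2 places subjects with zero follow-up in the Study Exit score summaries and shift tables as unchanged. It also leaves two defensible results for change from baseline. It conflicts in spirit with the observed-data rule in SAP 6.2.1 and Protocol 14.4.

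The effect on shift percentages is a factor of (n − k)/n. Overall it is small unless several subjects are concerned, and it is larger in the breakdown by last SAKURA dose. It is nil if k = 0. The result rests on the pre-injection Day 1 record being used for shift, and the group sizes of 20 and 10 are assumptions. This should be fixed: the rule is wrong for a long-term safety display, and the ophthalmoscopy and cataract shift tables have no Month 12 version beside them.

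**What to change.** - **SAP 4.1.2:** delete the sentence that makes Day 1 the exit visit. Deletion alone is not enough, because the fallback to the last visit before the exit date would still select Day 1. State that a subject with no assessment after Day 1 has no Study Exit score, change or shift. Label results from the fallback rule as last observed value.
- **SAP 4.2.3:** add that shift from baseline, like change, is derived only at a post-baseline visit.
- **SAP 8.2 to 8.5:** in each exit table, add a row with the number of subjects without a post-baseline assessment, by last SAKURA dose and overall.
- **SAP 7.1:** state that a Day 1-only subject does not count as having completed the study exit assessment. The current text does not settle this.

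The cost is a few lines of SAP text, one extra row per exit table and a slightly smaller n. No data collection changes. The outcomes of these subjects stay unknown, but the tables would then say so. If k = 0, no result changes.

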#### 4.1.3. Study Day / Days on Study / Days on Treatment

The *study day* variable describes the relative day of the observation starting with Day 1 as the reference date. There will be no Day 0. The study day will be calculated as follows:

- For events occurring on or after the reference date

$$\text{Study Day} = (\text{Date} - \text{Baseline Visit Date}) + 1$$

- For events occurring before the reference date

$$\text{Study Day} = (\text{Date} - \text{Baseline Visit Date})$$

*Days on Study* measures the duration each subject remains in the study and will be calculated as follows:

$$\text{Days on Study} = (\text{Study Exit Date} - \text{Baseline Visit Date}) + 1.$$

*Days on Treatment* measures the duration between the date of first exposure to DE-109 and exit date of each subject and will be calculated as follows:

$$\text{Days on Treatment} = (\text{Study Exit Date} - \text{Date of First Exposure to Treatment in SPRING Study}) + 1.$$

